Location of study conduct	
Each subject will participate in the study in the participating organization by which the subject is employed:
 
• SI National Institute of Phthisiology and Pulmonology named after F.G. Yanovsky.• Yuria-Pharm LLC.• Infuzia PJSC.• Institute Hyalual LLC.• Medical Center M.T.K. LLC.• InterChem SLC.• Diatom LLC. 
For the study the following facilities will be organized at each participating organization:
 
• Specially designated locations for material collection and conduction of rapid ELISA tests for the antibodies to COVID-2019.• Specially designated computerized places for questionnaires with assigned staff who organize the order and accuracy of the questionnaire conduct.
Duration of data collection	3 months.
Purpose of the study	To determine the relationship between the systematic use of prophylactics to prevent SARS, including COVID-2019, and the risks of incidence and serious complications of COVID-2019 among staff of participating organizations.
Study objectives	
• To investigate the incidence of COVID-2019 cases in participating organizations.• To investigate the severity of the COVID-2019 cases in participating organizations.• To explore the prevention methods used by staff members.• To determine the relationship between the used prevention methods and incidence of COVID-2019 among staff of participating organizations.

	
• To determine the relationship between the presence of comorbidities, such as bronchial asthma and COPD, and the incidence/severity of COVID-2019.• To determine the relationship between the COVID-2019 case and the course of comorbidities, such as bronchial asthma and chronic obstructive pulmonary disease (COPD).• To identify the relationship between different strategies and combinations of drugs used for prophylactics at any time from March 2020 and the risk of having a COVID-2019 case.• To identify the relationship between different strategies and combinations of drugs used for prophylactics at any time from March 2020 and the risk of having a severe COVID-2019 case.• To identify the relationship between different strategies and combinations of drugs used for prophylactics at any time from March 2020 and the risk of hospitalization of persons who had at least one COVID-2019 case.

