Study limitations	
Persons, who were employed by one of the participating organizations from March 1, 2020, but who do not have employment relations with the participating organizations during the study period or persons who are on maternity leave, will not be included in the study.
 
Another study limitation is duration of data collection (due to long-term data collection there is a difference in the duration of action of the exposure factor).
 
The retrospective study design has limitations on the completeness and accuracy of the data provided by the study subjects.
 
There may be difficulties in filling in the missing data.
 
Certain relationships can be difficult to describe.
 
The direction of the relationship cannot be determined for all relationships (there may be an inverse relationship).
 
Potential data distortion may be due to the subject selection; use of an electronic data collection system; possible low computer literacy of some subjects; lack of data verification and query generation.
 
The completeness and correctness of the description of available medical documentation for fatal cases of COVID-2019 depends on the amount of information provided and its quality. Conclusions from it cannot be extended to other population members.

-------------------	---

Statistical analysis plan

In the context of this data analysis, all the main steps from the primary data to the results of the study will be described separately in the Statistical Analysis Plan.

This study is not intended to accept or reject pre-defined hypotheses, thus statistical analysis will mainly be descriptive.

All types of analysis will be done for the entire available study population with available data.

If there is a sufficient amount of data in the subpopulations, a separate statistical analysis will be performed.

No conditional calculation methods will be applied to the missed values.

The statistical generalization will consist of frequency tables of categorical variables (number, %).

For metric variables, descriptive statistics (number of subjects with available observations, number of missed values, mean, standard deviation, median, 25th and 75th percentiles, minimum and maximum) will be presented in tabular form.

Statistical conclusions will be used to assess the potential relationship between the identified variables and the incidence / severity of COVID-2019.

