The relationship between the subject's characteristics and the variables of interest will be assessed using a one-dimensional and multidimensional (polynomial) logistic regression model for variables, which have no more than 20% omitted data.

The final model will be selected with a view to minimizing the Akaike information criterion value.

2×2 tables, χ^2 -square were used for calculations of odds ratios.

Rough odds ratios and adjusted odds ratios with corresponding 95% confidence intervals and p-values will be generated and presented for both one-dimensional and multidimensional logistics models.

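### Minimum-AIC selection of the final logistic model does not protect the prophylaxis exposure or any confounder, so the adjusted prophylaxis odds ratio can drop out or be distorted

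*Combined protocol and SAP*

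**What the plan says.** All references are to the Combined protocol and SAP.

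- **Purpose of the study** names the exposure: "To determine the relationship between the systematic use of prophylactics to prevent SARS, including COVID-2019, and the risks of incidence" and serious complications. Study objectives adds strategies and combinations of drugs in relation to having a case, having a severe case, and "the risk of hospitalization of persons who had at least one COVID-2019 case".
- **Statistical analysis plan** admits to the univariable and multivariable logistic models any variable with at most 20% missing data. It then says: "The final model will be selected with a view to minimizing the Akaike information criterion value".
- The same section says that crude and "adjusted odds ratios with corresponding 95% confidence intervals and p-values will be generated and presented", for both the univariable and the multivariable models. It does not say whether a multivariable model from before selection will be shown.
- On inferential status it says both "This study is not intended to accept or reject pre-defined hypotheses, thus statistical analysis will mainly be descriptive" and "Statistical conclusions will be used to assess the potential relationship between the identified variables and the incidence / severity of COVID-2019".
- On detail it says that "all the main steps from the primary data to the results of the study will be described separately in the Statistical Analysis Plan". That separate plan is not among the documents supplied.

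No section names a term that must remain in the model.

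**The concern.** AIC is a criterion for prediction. It does not know that one term is the question and that others are there to control confounding. Applied to every candidate term, it treats prophylaxis as any other predictor, which has three possible consequences:

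1. The adjusted prophylaxis odds ratio may be absent from the final model.
2. If the true effect is null or weak and the term survives, it survived because the estimate happened to be large. The estimate is then inflated and the ordinary interval under-covers.
3. The confounders adjusted for depend partly on chance.

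In a retrospective, non-randomised study the adjusted odds ratio carries most of the weight for the stated purpose, because the crude one has no control for confounding.

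**Working it through.** **Inputs.** N = 3443 (Number of subjects), the minimum-AIC rule and the 95% level come from the document. It gives no incidence, exposure prevalence, effect size, hospitalisation fraction or strength of confounding, so these are assumptions shown as ranges. There is no planned power figure to reproduce, since the sample size calculation is declared not applicable.

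**Deletion rule.** Removing a term with k degrees of freedom lowers AIC when its likelihood-ratio chi-square is below 2k. For a binary exposure (k = 1) the cut is |Z| < √2 = 1.414, or p > 0.157.

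**Probability of deletion, incidence outcome.** With incidence p and exposed fraction e, z = |ln OR| × √(N p(1−p) e(1−e)). The probability of deletion is the noncentral chi-square CDF (1 df, noncentrality z²) at 2. For OR 0.8, p = 0.2, e = 0.5: z = 0.223 × √(3443 × 0.16 × 0.25) = 2.62, giving 11.4%.

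| True OR | p=5%, e=10% | p=20%, e=10% | p=20%, e=50% | p=40%, e=50% |
|---|---|---|---|---|
| 0.9 | 80.9% | 73.4% | 56.7% | 45.8% |
| 0.8 | 70.0% | 43.6% | 11.4% | 3.6% |
| 0.7 | 51.6% | 13.6% | 0.3% | 0.01% |
| 0.6 | 29.2% | 1.5% | <0.001% | <0.001% |

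Fitted logistic models with three confounders (1000 runs) gave 71-72%, 44%, 12-13% and 3-4% for the OR 0.8 row.

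**Hospitalisation among cases.** The same formula is used with n = 3443 × incidence, 3-10% of cases hospitalised and OR 0.6. With half exposed, deletion runs from 77.7% (3443 × 0.05 × 0.03 = 5.2 events) to 7.6% (3443 × 0.40 × 0.10 = 137.7 events). With 10% exposed it runs from 81.9% to 38.4%. These are large-sample approximations and are rough at the low end.

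**Multi-level exposure.** Strategies and combinations may need several parameters. If such a term is kept or deleted whole, then at the same noncentrality (z = 2.62) deletion is 11% for 1 df, 20% for 2 df and 44% for 5 df.

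**Coverage if kept, single term, no confounder selection.** With Z ~ N(z, 1), coverage given retention is P(|Z−z| < 1.96 and |Z| > 1.414) / P(|Z| > 1.414).

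| z | Kept | Coverage if kept | Mean estimate ÷ truth |
|---|---|---|---|
| 0 | 15.7% | 68.2% | – |
| 1 | 34.7% | 90.5% | 2.0 |
| 1.5 | 53.6% | 95.0% | 1.5 |
| 2 | 72.1% | 96.5% | 1.2 |

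Over the same incidence and exposure ranges, z = 1 corresponds to an OR of 0.77 to 0.93, and z = 1.5 to 0.68 to 0.90.

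**Confounder also open to selection.** All-subsets AIC was simulated with one confounder and a null exposure (1500 runs). At N = 3443 the exposure was kept in 15.5-18.3% of runs, with coverage of 52-56% when kept. The unconditional error is then 0.155 × 0.476 = 7.4% and 0.183 × 0.438 = 8.0%, against a nominal 5%.

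**Exposure forced in, confounders chosen by AIC.** Simulation used a null exposure, 40% exposed, six confounders with outcome OR 1.08 or 1.15 per SD, incidence 5, 20 and 40%, and 600 runs per setting (Monte Carlo SE about 0.9 points). Coverage lost relative to the fixed full model:

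| Exposure–confounder log-OR per SD | Loss (points) |
|---|---|
| 0.1 | 0-0.2 |
| 0.3 | 0-2.5 |
| 0.7 | 0.5-11 |

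**The case against.** **AIC may be meant only to compare models that contain the exposure.** The section describes no stepwise or term-deletion procedure, so this reading is open. On it, deletion and the coverage loss from conditioning on retention both disappear. What stands is the AIC choice of confounders, which costs little unless exposure and confounders are strongly associated.

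**Odds ratios are promised for multivariable models in general.** A reader might infer from the AIC rule that the adjusted prophylaxis odds ratio will go unreported. The document does not support that: a model fitted before selection could also be presented. Equally, it does not say that one will be.

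**The analysis is mainly descriptive, and details are deferred.** Both statements are in the document and lower the severity. Neither withdraws the rule, and the same section draws statistical conclusions and reports intervals and p-values. It cannot be said that the separate plan lacks the protection, only that it must add it.

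**Strong effects survive.** This is largely true for incidence: at OR 0.6 deletion is 1.5% or less at 20% incidence. It is not general, since the figure is 29% at 5% incidence with 10% exposed, and higher still for hospitalisation with few events.

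**Conclusion.** The concern holds as a gap that should be closed. The stated rule, applied to all terms, can leave the adjusted prophylaxis odds ratio out of the final model. Deletion probabilities for a binary exposure are 46-81% at OR 0.9, 4-70% at 0.8, 0.01-52% at 0.7 and up to 29% at 0.6, and about 8-82% for hospitalisation at OR 0.6. All rest on the assumed ranges above.

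Three wider inferences are not supported:

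- **That every adjusted interval is invalid.** Conditional under-coverage is confined to null or weak effects, below about z = 1.5. Some inflation of the estimate persists beyond that, about 1.2 times at z = 2.
- **That the overall null error is safely 5%.** That is so for a single term with no other selection. Once confounders are also selected, it can exceed 5%, and coverage given retention at the null is about 52-68%.
- **That hospitalisation must have the fewest events of all outcomes.** The document gives no counts, and severe disease could have fewer.

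Crude odds ratios are not affected.

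**What to change.** For each prophylaxis–outcome odds ratio, state that:

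- the exposure is forced into the model;
- adjustment uses a set fixed in advance from variables already collected or known by design, for example age, sex, BMI, household size, lifestyle, asthma, COPD or other comorbidity, and organisation;
- a specified rule applies if one of these exceeds the 20% missing-data limit;
- severity and hospitalisation use a smaller fixed set (for example age, sex, any comorbidity), with a Firth penalised fit and an exploratory label where events are few;
- AIC is confined to optional terms or a sensitivity analysis, with models compared on one common set of rows and the resulting intervals and p-values labelled exploratory.

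The common-rows condition is a safeguard. The plan says "All types of analysis will be done for the entire available study population with available data", and AIC values from different rows are not comparable, but it does not say that different rows would be used.

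**Cost.** A few sentences, no new data and slightly wider intervals. The full set is about 16 parameters with a binary exposure, more if items have several levels. For incidence that gives 3443 × 0.05 / 16 = 10.8 cases per parameter at 5% incidence and 86 at 40%. For hospitalisation it gives only 0.3-8.6 events per parameter. A four-parameter set gives 1.3-4.3 at 5% incidence and 10-34 at 40%, hence the penalised fit. In 1000-run simulations of the four-parameter model at OR 0.6, maximum likelihood had no finite fit in 46% of runs at 5% incidence with 3% hospitalised and half exposed. Firth profile intervals covered 94.2-97.3% across 14 settings. The penalised fit adds no information, so those intervals will still be wide.

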Project code	EpidProtect-21
Study title	Exhaustive, cross-sectional, non-interventional, multicenter retrospective epidemiological study of the COVID-2019 incidence and prevention methods of SARS, including COVID-2019, among staff of participating organizations.
Version of Synopsis	0.2, 15.02.2021.
Justification of study	
Coronaviruses are a large family of viruses that might cause illness in animals or humans. SARS-CoV-2 is an enveloped, single-stranded RNA virus of the β genus. It can cause respiratory illness named COVID-19, the severity of which varies from asymptomatic to severe, and which can lead to the patient's death or long-term consequences (so-called post-COVID syndrome). The virus has spread globally and been declared a Public Health Emergency of International Concern by WHO in January 30, 2020.
 
The first case of COVID-19 in Ukraine was detected in early March, 2020. 1273475 cases of the disease have been registered in Ukraine as at February 15, 2021.
 
Quarantine restrictions and other anti-epidemic measures established in Ukraine and their results are the subject of wide debate.
 
Own anti-epidemic measures, in addition to those established by the Government, have also been implemented by numerous representatives of the public sector, non-governmental organizations and business.
 
The company management of the participating organizations decided to provide their staff with prophylactic tools and recommendations for COVID-19 prevention.
 
The study aims to identify the incidence, characteristics of cases and their relationship with the preventive measures used.

Study design	Exhaustive, cross-sectional, non-interventional, multicenter retrospective epidemiological study, case study.
Number of subjects	3443 subjects.

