Study endpoints	
• The incidence of COVID-2019 cases in participating organizations.• The severity of the COVID-2019 cases in participating organizations.• Prevention methods of SARS, including COVID-2019, which were used by subject who had at least one COVID-2019 case.

	
Prevention methods of SARS, including COVID-2019, which were used by subject who did not have any COVID-2019 case.Relationship between the used prevention methods and incidence of COVID-2019 among staff of participating organizations.Relationship between the presence of comorbidities, such as bronchial asthma and COPD, and the incidence/severity of COVID-2019 case.Relationship between the COVID-2019 case and the course of comorbidities, such as bronchial asthma and chronic obstructive pulmonary disease (COPD).Relationship between different strategies and combinations of drugs used for prophylactics at any time from March 2020 and the risk of having a COVID-2019 case.Relationship between different strategies and combinations of drugs used for prophylactics at any time from March 2020 and the risk of having a severe COVID-2019 case.Relationship between different strategies and combinations of drugs used for prophylactics at any time from March 2020 and the risk of hospitalization of subjects who had at least one COVID-2019 case.
Study variables	
Demographic characteristics: age, gender.Anthropometric characteristics: body weight, height.Blood group.Number of people in the household.Lifestyle: the presence of bad habits, physical activity, diet.Medical history: comorbidities, their treatment.Prevention methods of SARS, including COVID-2019, currently used by the subject.Number of COVID-2019 cases, which subject had.Characteristics of the disease case, its treatment.

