	
Prevention methods of SARS, including COVID-2019, which were used by subject who had at least one COVID-2019 case.Prevention methods of SARS, including COVID-2019, which were used by subject who did not have any COVID-2019 case.Amount of costs spent on prevention and treatment of SARS, including COVID-2019.Relationship between different strategies and combinations of drugs used for prophylactics at any time from March 2020 and the risk of having a COVID-2019 case.Relationship between different strategies and combinations of drugs used for prophylactics at any time from March 2020 and the risk of having a severe COVID-2019 case.Relationship between different strategies and combinations of drugs used for prophylactics at any time from March 2020 and the risk of hospitalization of subjects who had at least one COVID-2019 case.
Inclusion criteria	Subjects who meet all the inclusion criteria will be included in the study: 
The subject gave the consent to participate in the study and signed the consent to processing of personal data.The subject aged 18 years and older.The subject is employed by one of the participating organizations.
Exclusion/withdrawal criteria	The nature of the study does not provide for withdrawal criteria. The subject may not be included in the study due to non-compliance with the inclusion criteria or due to force majeure.
Calculation of sample size	Not applicable as it is exhaustive study. Participating organizations undertake to organize the involvement in the study of at least 95% of persons employed by participating organizations.

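### The drug-strategy endpoints have no common untreated reference: on a literal reading, the planned 2×2 odds ratios set each strategy against a mix of non-users and users of other strategies

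*Combined protocol and SAP*

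**What the plan says.** All references are to the combined protocol and SAP.

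- **Study endpoints.** One endpoint is "Relationship between different strategies and combinations of drugs used for prophylactics at any time from March 2020 and the risk of having a COVID-2019 case". Two parallel endpoints concern severe cases, and hospitalisation among people who had a case. The exposure therefore has several categories.
- **Purpose of the study.** The aim is "To determine the relationship between the systematic use of prophylactics to prevent SARS, including COVID-2019, and the risks of incidence" and serious complications. The purpose speaks of systematic use, whereas the endpoints count use at any time since March 2020.
- **Statistical analysis plan, tables.** "2×2 tables, χ^2 -square were used for calculations of odds ratios". Rows, columns and comparator are not described.
- **Statistical analysis plan, population.** "All types of analysis will be done for the entire available study population with available data". The next sentence allows separate analyses in subpopulations where there are enough data.
- **Statistical analysis plan, models.** It plans a "one-dimensional and multidimensional (polynomial) logistic regression model for variables, which have no more than 20% omitted data" and selects the final model by the smallest Akaike criterion. "Rough odds ratios and adjusted odds ratios with corresponding 95% confidence intervals and p-values" will be presented.
- **Justification of study.** Management "decided to provide their staff with prophylactic tools and recommendations for COVID-19 prevention". Uptake is not given.

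No section lists the exposure categories, says how people who used several products are classified, or names a reference group for the strategy endpoints.

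**The concern.** A 2×2 table has room for two exposure groups. If everyone stays in the table and the row is a particular strategy, the other row is all staff not on that strategy. That row holds people who took nothing together with people on every other drug or combination.

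The resulting odds ratio does not estimate the strategy against no prophylaxis. It also depends on what the rest of the staff took, so it can change with uptake of other products even when the strategy's own effect does not. Each strategy has a different comparator, so a list of such odds ratios cannot be used to rank strategies, which is what readers will want to do with these endpoints.

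Occasional users are a related gap. The purpose concerns systematic use, but nothing says whether someone who took a product now and then counts as a user, a non-user or neither.

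**Working it through.** **Inputs.** The plan gives no event count, effect size or uptake for these endpoints, so there is no figure of its own to reproduce. Only N = 3443 comes from the documents (Number of subjects). Risks, odds ratios and shares below are assumptions.

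**Formula.** Let p0 be the risk in non-users and odds(p) = p/(1 − p). A regimen with true odds ratio R against no drug has odds R × odds(p0). The 2×2 result is odds(risk in regimen) ÷ odds(share-weighted mean risk in everyone else).

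**Case 1: four mutually exclusive, equally common regimens, each R = 0.60, p0 = 0.20.**
- Regimen odds = 0.25 × 0.60 = 0.15, so risk = 0.15/1.15 = 0.1304.
- With 20% non-users, each regimen has 20% of staff. Mean risk in the rest = (0.60 × 0.1304 + 0.20 × 0.20)/0.80 = 0.1478, with odds 0.1735.
- Apparent OR = 0.15/0.1735 = 0.86, against a true 0.60.
- If the regimen of interest is inert (R = 1) and the other three keep 0.60, the apparent OR = 0.25/0.1735 = 1.44.

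| Non-users | Mean risk in the rest | Apparent OR, true 0.60 | Apparent OR, true 1.00 |
|---|---|---|---|
| 10% | (0.675 × 0.1304 + 0.10 × 0.20)/0.775 = 0.1394 | 0.93 | 1.54 |
| 20% | 0.1478 | 0.86 | 1.44 |
| 40% | (0.45 × 0.1304 + 0.40 × 0.20)/0.85 = 0.1632 | 0.77 | 1.28 |
| 60% | (0.30 × 0.1304 + 0.60 × 0.20)/0.90 = 0.1768 | 0.70 | 1.16 |

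Taking p0 as 10% or 30% moves these by at most about 0.01.

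**Case 2: two drugs used independently.** Each has R = 0.50, p0 = 0.20, with 25% of staff in each of the four cells. Risk is 0.1111 on one drug and 0.0588 on both.
- A users: (0.1111 + 0.0588)/2 = 0.0850, odds 0.0929.
- Not A: (0.20 + 0.1111)/2 = 0.1556, odds 0.1842.
- OR = 0.504, so almost no distortion for the single drug.

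**Case 3: the combination as the exposure, under independent use.** Two drugs each have R = 0.60, so the combination has R = 0.36, odds 0.25 × 0.36 = 0.09.
- Uptake 25% each: the rest have risk (0.5625 × 0.20 + 0.375 × 0.1304)/0.9375 = 0.1722, odds 0.2080. Apparent OR = 0.09/0.2080 = 0.43.
- Uptake 70% each: (0.09 × 0.20 + 0.42 × 0.1304)/0.51 = 0.1427, odds 0.1665. Apparent OR = 0.54.

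Independent use protects the single-drug odds ratio but not that of the combination.

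**Case 4: inert drug A, drug B with R = 0.50, p0 = 0.20.**
- Mostly taken together (40% both, 40% neither, 10% each alone): A users (0.10 × 0.20 + 0.40 × 0.1111)/0.50 = 0.1289; not A (0.40 × 0.20 + 0.10 × 0.1111)/0.50 = 0.1822. OR = 0.1480/0.2228 = 0.66, falsely protective.
- Never together (40% A, 40% B, 20% neither): rest (0.40 × 0.1111 + 0.20 × 0.20)/0.60 = 0.1407. OR = 0.25/0.1638 = 1.53, falsely harmful.

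**Case 5: no regimen has any association.** All risks are equal and every OR is 1.00.

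**The case against.** The strongest reply is that the used / not-used coding is nowhere stated. The 2×2 sentence is not tied to prophylaxis; it could serve the asthma and COPD comparisons, or a regimen against non-users only. The whole-population sentence may just define the analysis set, and the subpopulation sentence leaves room for restricted tables. The logistic models can hold several drug terms or a multi-category exposure. The analysis is called mainly descriptive, and its detailed steps are deferred to a separate plan. Management supplied tools and recommendations, which need not mean drugs and says nothing about uptake, so a small non-user group is conjecture.

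Much of this stands. The coding is an inference, and the models must be counted as part of the plan. The reply does not close the gap, for four reasons:

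- A table of one regimen against non-users must drop users of all other regimens. That sits badly with the whole-population rule, and the subpopulation sentence does not name such a restriction. A table of any drug against none keeps everyone but does not address different strategies.
- No reference category is named for the models either, and selection by the Akaike criterion may remove the terms for other regimens. Crude odds ratios are reported in any case.
- Descriptive or not, the odds ratios carry confidence intervals and p-values and are the means of answering the stated purpose.
- The announced separate plan is not among these documents, while the text here already sets the table format and the population.

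A reader might go further and infer that the plan definitely compares each regimen with users of the others, so that effective regimens will look weak and inert ones harmful. The documents do not support that. They do not state the coding, and Cases 2, 4 and 5 show that the distortion can be negligible, reversed or absent.

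**Conclusion.** The point holds as a conditional one that should be corrected. The plan offers a two-group table for a many-group exposure, keeps everyone in the analysis, and fixes no untreated reference in the tables or the models. On the literal reading, crude odds ratios for strategies can be biased and cannot be compared with one another.

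The size rests wholly on assumed use patterns. With four equal, mutually exclusive regimens and 10% to 60% non-users, a true 0.60 shows as 0.93 to 0.70. A two-drug combination with a true 0.36 shows as 0.43 to 0.54 at 25% to 70% independent uptake of each drug. The direction can go either way for an inert drug (0.66 or 1.53), and the distortion is small if most staff used nothing. Whether any of this arises depends on patterns of co-use and a share of non-users that the documents do not give.

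**What to change.** For the three strategy endpoints, replace the 2×2 tables with 2×k tables on a single exposure variable with mutually exclusive categories:

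- no prophylactic drug (the reference);
- each common single drug or combination;
- all rarer combinations, pooled;
- occasional use only, as a separate category where the collected data allow it.

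Keep this variable in the logistic models regardless of the Akaike criterion. Report crude and adjusted odds ratios for every category against the same reference. State in advance that the most common regimen will be a second fixed reference if non-users are few.

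The cost is SAP wording and recoding of prophylaxis data that the study collects anyway. The price in precision is real. As an illustration under Case 1 with 10% non-users, N = 3443 gives about 344 untreated and 775 per regimen:

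- Against the untreated (about 69 and 101 cases), the standard error of the log odds ratio is √(1/69 + 1/275 + 1/101 + 1/674) = 0.172.
- Against all 2668 others (about 372 cases), it is √(1/101 + 1/674 + 1/372 + 1/2296) = 0.120.

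The interval on the log scale is about 1.4 times as wide, but it is centred on the contrast with no prophylactic drug (0.60 in that example) rather than on 0.93.

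### Intervals and p-values for prophylaxis exposures may be anti-conservative, because the plan names no employer term and makes no allowance for correlation between co-workers

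*Combined protocol and SAP*

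**What the plan says.** The Statistical analysis plan section names two routes to an odds ratio. One is the 2×2 table with chi-square, which "were used for calculations of odds ratios". The other is univariable and multivariable logistic regression, with the final model chosen by the Akaike information criterion (AIC). On output it says "Rough odds ratios and adjusted odds ratios with corresponding 95% confidence intervals and p-values will be generated and presented". On the analysis set it says "All types of analysis will be done for the entire available study population with available data".

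The section names no employer covariate, random effect, generalized estimating equation (GEE) or robust variance. Study limitations does not mention dependence between subjects.

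The data structure is given elsewhere. Number of subjects is "3443 subjects". Location of study conduct lists seven organizations and says "Each subject will participate in the study in the participating organization by which the subject is employed". Calculation of sample size aims for at least 95% of their employees. Justification of study says "The company management of the participating organizations decided to provide their staff with prophylactic tools and recommendations for COVID-19 prevention". Study variables lists household size, but no department, shift or team.

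**The concern.** Chi-square tests and ordinary logistic regression take one employee's outcome as uninformative about the next, given the covariates in the model. The outcome here is a contagious infection among people who work for the same organizations. Near-complete enrolment means that colleagues who infected one another will often both be in the data.

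The exposure may cluster too, because the employers' management supplied prophylactic tools and advice. When outcome and exposure are both alike within groups, the model-based standard error of the exposure's log odds ratio is too small. Two levels matter:

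- **Employer.** The documents point to this level directly, and the plan names no employer term.
- **Work unit within employer.** An employer term removes differences between employers. It does not remove outbreaks within a department or shift.

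At stake is the precision claimed for the study's stated purpose, the relation between prophylactics and COVID-19 risk. A chance association could be reported with an interval that covers less often than its label says.

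**Working it through.** The plan has no power, sample size or alpha calculation to reproduce; 3443 is a headcount.

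**Inputs from the documents.** N = 3443; 7 employers; 95% intervals, so a two-sided 5% test is implied. Average staff per employer is 3443/7 ≈ 492. Sizes per employer are not given.

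**Assumed inputs.** The documents give no ICC, work-unit size or exposure pattern. The ranges used are work units of 15–30, outcome ICC 0.02–0.10 and exposure ICC 0–1.

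**Formulas.** With m the group size:

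- DEFF = 1 + (m − 1) × ICC(outcome) × ICC(exposure)
- required widening of the interval (log odds ratio scale) = √DEFF
- actual size of a nominal 5% test = 2 × [1 − Φ(1.96/√DEFF)]

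**Employer not adjusted (m ≈ 492).**

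| ICC outcome | ICC exposure | DEFF | Width × | Actual size |
|---|---|---|---|---|
| 0.01 | 0 | 1.00 | 1.00 | 5.0% |
| 0.001 | 0.1 | 1.05 | 1.02 | 5.6% |
| 0.01 | 0.1 | 1 + 491 × 0.001 = 1.49 | 1.22 | 10.8% |
| 0.01 | 0.3 | 1 + 491 × 0.003 = 2.47 | 1.57 | 21.3% |

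**Employer adjusted, clustering left within work units.**

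| m | ICC outcome | ICC exposure | DEFF | Width × | Actual size |
|---|---|---|---|---|---|
| any | any | 0 | 1.00 | 1.00 | 5.0% |
| 15 | 0.02 | 0.3 | 1 + 14 × 0.006 = 1.08 | 1.04 | 6.0% |
| 15 | 0.05 | 0.3 | 1 + 14 × 0.015 = 1.21 | 1.10 | 7.5% |
| 20 | 0.05 | 0.3 | 1 + 19 × 0.015 = 1.29 | 1.13 | 8.4% |
| 30 | 0.05 | 0.3 | 1 + 29 × 0.015 = 1.44 | 1.20 | 10.2% |
| 30 | 0.05 | 1 | 1 + 29 × 0.05 = 2.45 | 1.57 | 21% |
| 30 | 0.10 | 1 | 1 + 29 × 0.10 = 3.90 | 1.97 | 32% |

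The last two rows require everyone in a unit to use the same prophylaxis. They mark the edge of the range and are not an expectation.

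**Simulation check.** Settings: N = 3443, employer fixed effects, true odds ratio 1, work units of 10 or 20, outcome ICC 0.05 or 0.10, 1000 runs per setting. The Monte Carlo standard error is about 0.7 percentage points.

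| ICC exposure | Ordinary standard error: actual size | Cluster-robust by work unit: actual size |
|---|---|---|
| 0 | 4.6–6.2% | 4.9–6.4% |
| 0.1 | 4.6–6.3% | 4.4–5.3% |
| 0.3 | 6.4–10.4% | 4.8–6.5% |

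The simulation agrees broadly with the formula. Ordinary standard errors are adequate when exposure is weakly clustered. They fall short at exposure ICC 0.3, where cluster-robust standard errors bring the error back close to 5%.

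**The case against.** The strongest reply has four parts.

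1. **The effect is conditional.** A reader might infer that every interval in the study is too narrow, even after adjusting for employer. The documents do not support that. The inflation is 1.00 when exposure does not cluster, so covariates such as blood group are essentially unaffected. Supply by management is an act at employer level, and no section describes departments, shared rooms or distribution by team. The study objectives refer to differing strategies and drug combinations, so individual variation in use is expected. This part stands, and it is why the point is worded as a possibility and puts the employer term first.

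2. **The department field may exist.** A reader might also infer that work unit is not recorded. The documents show only that it is not among the listed study variables. The case report form is not available here, and employer is not listed either, although it is known by design. This stands.

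3. **The study calls itself mainly descriptive and refers detail to a separate Statistical Analysis Plan.** That lowers the consequence, since no decision rule is stated. It does not remove the point. The plan promises intervals and p-values for relationships, and an interval labelled 95% should cover about 95% with or without a pre-defined hypothesis. A separate plan may deal with correlation, but it cannot cluster on a unit that was never obtained.

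4. **Replacing logistic regression by GEE would break the AIC selection.** GEE has no likelihood, so AIC would be undefined. This stands against GEE. It does not stand against robust standard errors on the same logistic models.

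**Conclusion.** The point holds in conditional form and should be acted on. As written, the plan leaves out employer and any allowance for correlation between co-workers, so the error bars for prophylaxis exposures can be anti-conservative.

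The better-supported part is the missing employer term: under assumed ICCs of 0.01 (outcome) and 0.1 (exposure), a 5% test has actual size of about 11%. With employer adjusted, what remains depends on clustering within work units. It ranges from nothing to a DEFF of 3.9, with about 6–10% error for moderate clustering (exposure ICC 0.3 in the simulation).

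Every ICC and work-unit size is an assumption, and the employer-level figure also takes the average staff size as common to all seven. The true effect may be small. The documents do not establish that intervals are in fact too narrow, nor that any covariate outside the clustered exposures is affected.

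**What to change.** In the Statistical analysis plan section:

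- Include employer as a fixed covariate in every prophylaxis model.
- Take department or work unit from the staff list, linked by the individual number each subject already has.
- Keep AIC selection on the ordinary logistic likelihood. Then report the selected model and the univariable models with cluster-robust (sandwich) standard errors by work unit, with a small-sample correction.
- Base crude p-values on the univariable logistic model instead of the chi-square test.
- Do not use robust variance at employer level; seven clusters are too few for it to be reliable.

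In Study limitations: where work unit cannot be obtained, or events are sparse (as may happen for severe cases and hospitalization), state that independence between employees of the same employer was assumed.

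The cost is one administrative field, a variance option on models already planned, and somewhat wider intervals.
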